1. SYNOPSIS

It may be useful to include a synopsis of the study for quick reference. Delete or alter as appropriate/required.

Study Title	Collection of Cervical Cells at Colposcopy using a novel technique for analysis of high risk vs. low risk lesions		
Internal ref. no.	R&D A094381		
Study Design	Observational & Lab Based		
Study Participants	Women referred to colposcopy with abnormal cytology or those requiring a cervical examination		
Planned Sample Size	800 in total		
Follow-up duration	Nil		
Planned Study Period	5 years		
Primary Objective	The aim of the project is to improve the collection and analysis of cells taken from the surface of the cervix in order to identify high risk or low risk cervical cancer precursor lesions		
Secondary Objectives	None		
Primary Endpoint	Demonstrating clear correlation of high/ low risk lesions with novel molecular techniques or achieving 800 samples (whichever is sooner)		
Secondary Endpoints			
Intervention (s)	Removing a layer of cells from the cervix with no trauma and preserving the spatial distribution of cells for analysis		

2. BACKGROUND AND RATIONALE

Outline the scientific justification for the research. Give an outline of the background to the study, with references to literature and other relevant research.

Give an outline of the main research questions. Give a brief outline of the intervention (if applicable) and summary of findings from previous studies (if relevant) that potentially have clinical significance.

Provide summary of the known and potential risks and benefits of any of the study procedures (where applicable)

Describe the population to be studied.

The aim of the project is to improve the collection and analysis of cells taken from the surface of the cervix in order to more accurately identify cervical disease when it is present. Cells taken from the surface of the cervix are currently sampled using a cytobrush or spatula as part of the cervical smear test. This approach scrapes and/or scarifies the surface of the cervix, and harvests a mixture of cells from the superficial to mid epithelial layers. Cytological abnormalities are subsequently identified from amongst these exfoliated cells by Papanicolau staining. The site and severity of cervical disease is then identified by colposcopy examination, and by pathology assessment of biopsies taken from areas where disease is suspected. In some instances, the areas of disease predicted by cytology can be difficult to identify at colposcopy, and in such instances, multiple biopsies may need to be taken.

Here we propose a modified approach in which cells are taken from the surface of the cervix using a 'filter-paper' disk of nylon (e.g. Sigma-Aldrich cat. Z134341) or cellulose (e.g. Sigma-Aldrich cat. Z612391 (nitrocellulose)/ cat Z61238/Z612359 (mixed cellulose esters)). In our modified approach, the disk of nylon or cellulose will be gently pressed onto the surface of the cervix in order to lift off a layer of exfoliating surface cells in their in situ positions. The morphology of the surface cells is indicative of underlying cervical disease, and this can then be assessed by cytological analysis. We have already demonstrated that this technique works in our original pilot study and our previous work has suggested that a small panel of biomarkers present at the surface of the cervix can identify both disease severity and (if used appropriately) HPV type. The two most significant of these markers are MCM, which is a marker of cells that are in cycle, and E4, which is an abundantly expressed viral protein. These two proteins change their distribution at the epithelial surface according to the severity of cervical neoplasia. MCM, and other similarly regulated proteins such as PCNA and Ki-67, are often regarded as surrogate markers of E7 expression when they are present in the supra-basal cell layers. E4 is a highly expressed viral protein, and represents a distinct class of biomarker, whose expression follows that of MCM during the productive HPV life cycle. A diagrammatic representation of how these proteins are expressed in cervical disease of different grades is shown in Fig. 1A. The figure also demonstrates

the distribution of L1 which also represents a third discriminatory marker that is expressed in a sub-set of E4-positive cells in low-grade disease. Conversely, p16 is found in a subset of the MCM-positive cells in high-grade disease, and represents the fourth class of discriminatory marker that could be used in our system to identify potential pre-cancerous lesions as shown in Fig. 2A.

Fig 1A: Schematic representation of viral protein expression in CIN (Doorbar, John, et al. "Human papillomavirus molecular biology and disease association." *Reviews in medical virology* 25.S1 (2015): 2-23)

Using such an approach has a number of potential advantages over conventional methodologies. Firstly, it avoids scarification, which can act to spread virions present at the surface of LSIL and inoculate them at basal sites. In the Rhesus model of cervical disease, this scarification is a necessary event in the initiation of a new infection. Secondly, by keeping the exfoliated cells in their in situ positions will allow the position of cytological abnormalities, identified at the level of cytology or by immunostaining, to be localized to a particular cervical site. This should help to avoid some of the difficulties associated with the identification of disease areas at colposcopy, especially when lesion size is small. And thirdly, by combining this cell-collection approach with disease staging markers such as E4 and MCM, we will be able to more rapidly identify abnormal cells from the majority of cells with normal morphology, and provide a molecular assessment of disease severity at particular sites, which has the potential lead to more individualized treatment of these lesions.

Fig 2A. Immunohistochemistry staining using p16 (red) and E4 (green). p16 is a surrogate marker of E7 expression. The above image demonstrates that as a low-grade lesion transforms into a high-grade lesion (CIN 1 to 3), p16 staining is dramatically increased while E4 staining (associated with a productive infection) diminishes in intensity (Image courtesy of [name], HPV Lab, Department of Pathology, University of Cambridge)

The localization of cervical disease and the assessment of severity are key to accurate diagnosis and disease management. The approach suggested here is likely to be of value as an adjunct to colposcopy, and will also be useful in clinical trials such as those used to assess vaccine efficacy, where there is a need to monitor disease progression over time without taking biopsy specimens (which effectively remove the infected tissue, and prevents follow-up). This non-invasive sampling methodology should also provide new insight into aspects of papillomavirus disease, which are poorly understood, such as papillomavirus latency, re-activation and regression.

Alongside the assessment of this technique to better identify HPV positive women who truly have disease needing excision, another population of women that would perhaps benefit from this approach are those women who suffer with conditions such as post-coital bleeding or morphologically abnormal cervixes. These patients make up nearly 2/3rd of our colposcopy workload, the majority of whom go through the cancer 2 week wait pathway with considerable anxiety and out of these referrals approximately 1% of women would have clinically relevant disease^{6,7} in contrast to nearly 20-30% of HPV positive women that have such disease. Thus the ability to perform a diagnostic test as proposed here that can identify lesions at the outset would

have a multitude of advantages including preventing unnecessary referrals to the already overstretched colposcopy service and improve patient satisfaction by reassuring patients in a quicker and less intrusive manner.

There are no perceptible risks for the patient in this study. There are no direct benefits for the participant. Patients attending the colposcopy clinic will be asked to participate.

3. OBJECTIVES

There is usually only one primary objective, the rest are secondary objectives. The wording of the objectives should be clear, unambiguous and as specific as possible.

3.1 Primary Objective

The aim of the project is to improve the collection and analysis of cells taken from the surface of the cervix in order to identify high risk or low risk cervical cancer precursor lesions

3.2 Secondary Objectives: None

4. STUDY DESIGN

4.1 Summary of Study Design

Observational, Basic Science Study Duration: Up to 5 years

4.2 Primary and Secondary Endpoints/Outcome Measures

Demonstrating clear correlation of high/ low risk lesions with novel molecular techniques **or** achieving 800 samples (whichever is sooner)

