4.5 Definition of End of Study

The end of study is when we have either met our proposed primary objective or if we reach our maximum number of samples.

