7. STATISITICS

7.1 The Number of Participants

For the study, we envisage that 800 cell-lifts will be sufficient (with the majority being smear abnormal patients and approximately 50 patients being referred for clinical indications). Though this number has not been formulated by a formal power calculation, we envisage that this would certainly be an adequate number so as to get over certain hurdles such as obtaining a monolayer of cells on the membrane, staining with low level of background noise and demonstrating lesions.

During the first year of study we have recruited 105 patients. The majority of these patient samples have been used to create a standardized, reproducible protocol. This protocol has then been tested on 31 patients successfully with a corresponding sensitivity of 87% and positive-predictive value of 87%. We have now commenced a collaboration with [name] who has calculated that a sample size of 800 patients would give us a robust analysis of the true sensitivity, specificity, PPV and NPV of our diagnostic approach with narrow confidence intervals. As we have already recruited 105 patients, we would like to therefore increase the total number of patient during the study time to 800 in total. To effectively do this we would also require an increase in the duration of the study period to the end of April 2022. The end of April is referring to end of study recruitment and the sample analysis will be completed within a year after the recruitment is closed.

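### The primary endpoint and end-of-study rule accept either an undefined clear correlation or 800 samples, which conflicts with the accuracy aim and sample-size reasoning in Protocol 7.1 and 7.2

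*Protocol*

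**What the plan says.** The Protocol synopsis gives the primary endpoint as "Demonstrating clear correlation of high/ low risk lesions with novel molecular techniques or achieving 800 samples (whichever is sooner"), and section 4.2 repeats it, including the limb "achieving 800 samples (whichever is sooner"). Section 4.5 turns it into a stopping rule: "The end of study is when we have either met our proposed primary objective or if we reach our maximum number of samples". The objective that 4.5 refers to, in section 3.1, begins "The aim of the project is to improve the collection and analysis of cells taken from the surface of the cervix" and carries no measurable criterion.

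Section 7.1 gives the size two justifications. It first says "Though this number has not been formulated by a formal power calculation" and argues that 800 is enough to overcome technical hurdles. It then reports a collaborator's calculation that "a sample size of 800 patients would give us a robust analysis of the true sensitivity, specificity, PPV and NPV" with narrow confidence intervals. The same section reports that 105 women had been recruited in the first year and that the standardised method was "tested on 31 patients successfully with a corresponding sensitivity of 87% and positive-predictive value of 87" per cent. It moves the close of recruitment to the end of April 2022, with sample analysis completed within a year of that. Section 7.2 defers the analysis plan but names sensitivity, specificity and PPV/NPV corrected for prevalence.

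**The concern.** Two different things are joined by an either/or. One limb is a result with no statistic, threshold, reference cut-point or look schedule. The other is a head count. The count limb is satisfied by completing recruitment, so meeting the endpoint says nothing about whether the cell lift separates high-grade from low-grade disease.

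The result limb, taken with 4.5, allows recruitment to end when the accumulating data look good enough. If that were used, the sensitivity reported at the stop would tend to be too high, because a chance high value is what triggers the stop. It would also rest on fewer diseased women than 7.1 assumes. Section 2 presents the test as a way to avoid unnecessary colposcopy referrals. Overstated sensitivity in that use would mean missed disease.

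**Working it through.** **1. The passages side by side.**

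| Place | What decides the endpoint or the end of study |
|---|---|
| Synopsis, 4.2 | clear correlation, or 800 samples, whichever comes first |
| 4.5 | primary objective met, or maximum number of samples |
| 7.1 | 800 women, for narrow intervals on four accuracy measures; recruitment to end of April 2022 |
| 7.2 | sensitivity, specificity, PPV/NPV; correlation not mentioned |

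The first two rows permit fewer than 800 women on the strength of the results. The third needs all 800. The fourth analyses a different quantity from the one in 4.2.

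**2. The plan's own figure.** The 800 cannot be reproduced, because 7.1 states no interval width, confidence level or prevalence. It can be checked for plausibility. Assume a 95% interval, sensitivity 87% (the 31-patient value in 7.1) and 20–30% diseased (section 2 gives this for HPV-positive women; applying it here is an assumption).

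- Diseased women needed for half-width h: n = 1.96² × p(1 − p) / h². With p = 0.87 and h = 0.05: 3.8416 × 0.1131 / 0.0025 = 173.8, so 174.
- Total women = 173.8 / prevalence: 869 at 20%, 696 at 25%, 580 at 30%.

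So 800 fits a half-width of roughly 5 points for sensitivity.

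**3. Precision lost by an early stop.** Half-width = 1.96 × √(0.87 × 0.13 / diseased women):

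| Women at stop | Diseased at 20% / 30% | Half-width, points |
|---|---|---|
| 800 | 160 / 240 | 5.2 / 4.3 |
| 400 | 80 / 120 | 7.4 / 6.0 |
| 200 | 40 / 60 | 10.4 / 8.5 |

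**4. Bias if the study stops on a good look.** The Protocol fixes no threshold, look schedule or prevalence, so all three are assumed:

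- Threshold: stop at the first look with observed sensitivity of at least 87%, otherwise go to 800.
- Looks: every 50 women from 150, because 105 were already recruited.
- Prevalence: 23.5%, from 750 smear-abnormal women at 25% and 50 clinical referrals at 1%: (187.5 + 0.5) / 800 = 0.235.
- Alternative prevalence: 48%. The 31-patient tables (TP/FN/FP/TN) in which sensitivity and PPV both round to 87% are 13/2/2/14 and 20/3/3/5. The first has 15/31 = 48% diseased.

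Simulated results (20,000 studies per row) at true sensitivity 80%:

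| Looks | Diseased | Stop early | Mean sensitivity reported by early stops |
|---|---|---|---|
| Every 50 from 150 | 23.5% | about 22% | 89% |
| Every 50 from 150 | 48% | about 8% | 88–89% |
| 200, 400, 600 | 23.5% | about 13% | 89% |
| 400 only | 23.5% | about 4% | 88–89% |
| None (one analysis at 800) | 23.5% | 0% | not applicable; overall mean 80% |

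Averaged over all studies at 23.5% diseased, stopped early or not, the mean is 80.1% with the single look at 400 and 81.6% with looks every 50 from 150. The bias sits in the studies that stop.

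**5. The count limb.** This needs no arithmetic. Once 800 samples are collected, the condition in 4.2 is true for any sensitivity and specificity.

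**The case against.** The best defence is 7.1 itself. The investigators saw 87%/87% in 31 women and did not stop. They set the target at 800 for precision, extended recruitment to a date, and placed completion of the sample analysis after recruitment closes. That is close to what the fix asks for, so the fault is largely one of wording. This stands as evidence of intent, but it does not cancel 4.2 or 4.5, which still license a stop on results.

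A second defence is that a separate analysis plan may define the accuracy measures and what counts as clear. It may, but the endpoint and end-of-study rule are set in the Protocol and would remain.

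Several stronger readings are tempting and not supported:

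- **The study will report inflated accuracy.** A run to 800 with one analysis is unbiased. Inflation is conditional on an actual early stop.
- **The 31-patient result already met the rule.** No criterion exists to judge that by, and recruitment continued.
- **The study cannot fail.** It cannot fail on accuracy once 800 samples are in, but it could miss 800 by the deadline.
- **Early stopping is very likely.** Adding looks at 50 and 100 women raises the early-stop figure to about 40%, reporting 92%, but those points had passed once 105 were recruited.
- **Repeated looks inflate a type I error.** The Protocol states no hypothesis test or significance level, so there is no stated error rate to inflate.
- **Any one of several markers would do.** Section 4.4.2 names E4 with MCM as the stain, with p16 and p53 as a later refinement.

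**Conclusion.** The point holds as a conflict within the Protocol and should be fixed. Three things rest on the text alone: the count limb makes the primary endpoint independent of accuracy; the result limb permits a data-driven stop that would forfeit the precision given in 7.1 as the reason for 800; and correlation is not what 7.2 analyses.

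The size of any bias is uncertain and conditional. Under the assumed looks, 87% threshold and prevalence, with true sensitivity 80%, between about 4% and 22% of studies stop early, and those overstate sensitivity by roughly 9 points (89% against 80%). The loss of precision is firmer: a stop at 200 women about doubles the half-width, from 4.3–5.2 to 8.5–10.4 points. Given that recruitment continued past a favourable result, this is a rule to correct rather than evidence that the results are compromised.

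**What to change.** - **Synopsis and 4.2:** replace the present endpoint with the sensitivity and specificity of the cell-lift call for high-grade disease against histology, with 95% confidence intervals, analysed once after recruitment closes. State 800 as the sample size, not as part of the endpoint.
- **4.5:** let recruitment end only on 800 women or the end of April 2022 already given in 7.1. Delete the option to stop because the primary objective has been met.

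The cost is rewording in three places. No extra women, visits or samples follow from it. What is given up is the option to stop early on good results.

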4.3 Study Participants

4.3.1 Overall Description of Study Participants

Female participants with screen detected abnormal cervical cytology varying from mild dyskaryosis to severe dyskaryosis aged 25 to 65 years (with these ages corresponding to that of women that are eligible to be part of the cervical cancer screening programme.

Alongside this we will also aim to recruit all women referred to colposcopy with post-coital or abnormal bleeding that requires a cervical evaluation or a visually abnormal looking cervix

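### Section 4.3.1 recruits clinical-indication referrals without a limit while section 7.1 plans about 50 of 800; following 4.3.1 could cut the number of diseased women up to about 2.6-fold and widen the sensitivity interval up to about 1.6-fold

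*Protocol*

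**What the plan says.** Three parts of the protocol bear on the mix of women recruited.

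- **Section 4.3.1** describes women with abnormal screening cytology and then adds that "we will also aim to recruit all women referred to colposcopy with post-coital or abnormal bleeding", or with a visually abnormal cervix. It gives no number or limit. Neither the inclusion criteria in 4.3.2 nor the synopsis supplies one.
- **Section 7.1** sets the total at 800, "with the majority being smear abnormal patients and approximately 50 patients being referred for clinical indications".
- **Section 2** says of the clinical-indication group: "These patients make up nearly 2/3rd of our colposcopy workload". It adds that "approximately 1% of women would have clinically relevant disease", in contrast to "nearly 20-30% of HPV positive women that have such disease".

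Sections 4.2 and 4.5 end the study at 800 samples at the latest.

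On the reason for 800, section 7.1 first says that "this number has not been formulated by a formal power calculation". It then reports a collaborator's calculation that "a sample size of 800 patients would give us a robust analysis of the true sensitivity, specificity, PPV and NPV", with narrow intervals. It gives no interval width, prevalence or number of diseased women. Section 7.2 plans to adjust the accuracy measures to population prevalence.

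**The concern.** The precision of a sensitivity estimate depends on the number of diseased women, not on the total of 800. That number depends on how many places go to cytology referrals and how many to a group with about 1% disease. Sections 4.3.1 and 7.1 give different answers, and no operative rule in the protocol delivers the 7.1 split.

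Accuracy with narrow intervals is the reason given for raising the total to 800 and extending recruitment. Staff who follow 4.3.1 could reach 800 with well under half the diseased women that 7.1 implies. Once recruitment has closed, no analysis can recover them.

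**Working it through.** **Can the plan's figure be reproduced?** No. Section 7.1 gives no width, confidence level or prevalence from which to rebuild 800. As an illustration only, a half-width of 5 points at 87% sensitivity needs 0.87 × 0.13 × (1.96/0.05)² = 173.8, so 174 diseased women. At the 7.1 mix, with pooled prevalence of 18.8%, 23.5% or 28.2%, that means a total of 925, 740 or 617. So 800 is plausible for the 7.1 mix, but this is not a derivation of it.

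**Can 50 be what recruiting all of them yields?** If clinical-indication women are two thirds of the workload and cytology referrals the other third, then while 750 cytology women accrue, about 750 × (2/3)/(1/3) = 1,500 clinical-indication women attend. At equal uptake that many would enter, not 50. This step needs no prevalence figure.

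**Inputs**
- Total 800, about 50 of them clinical referrals, hence about 750 cytology referrals (section 7.1).
- Clinical-indication share 2/3, hence 533 and 267 of 800 (section 2; assumes recruitment in proportion to workload).
- Disease 1% in clinical-indication referrals (section 2).
- Disease p = 20%, 25% or 30% in cytology referrals. Section 2 gives 20-30% for HPV-positive women, and its use here is an assumption.
- Sensitivity 87% (first-year result in 31 patients, section 7.1). The 95% level is an assumption.

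**Formulas**
- Diseased women: n = (cytology referrals × p) + (clinical referrals × 0.01).
- Half-width for sensitivity: 1.96 × √(0.87 × 0.13 / n).

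At p = 25%:
- 7.1 mix: 750 × 0.25 + 50 × 0.01 = 188. Half-width 1.96 × √(0.1131/188) = 4.8 points.
- Workload mix: 266.7 × 0.25 + 533.3 × 0.01 = 72. Half-width 1.96 × √(0.1131/72) = 7.8 points.

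| | p = 20% | p = 25% | p = 30% |
|---|---|---|---|
| Diseased, 7.1 mix (750/50) | 150.5 | 188 | 225.5 |
| Diseased, workload mix (267/533) | 58.7 | 72 | 85.3 |
| Ratio of diseased women | 2.57 | 2.61 | 2.64 |
| Sensitivity half-width, 7.1 mix (points) | 5.4 | 4.8 | 4.4 |
| Sensitivity half-width, workload mix (points) | 8.6 | 7.8 | 7.1 |
| Ratio of half-widths | 1.60 | 1.62 | 1.63 |

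**Specificity.** Non-diseased women rise from 612 to 728 at p = 25%. For any fixed specificity the half-width changes by √(612/728) = 0.92, so it becomes about 8% narrower. The protocol gives no specificity value, and the ratio does not need one.

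**How far it depends on uptake** (p = 25%, against 188 diseased women):

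| Scenario | Diseased women | Case ratio | Interval ratio (square root) |
|---|---|---|---|
| 200 clinical referrals | 600 × 0.25 + 200 × 0.01 = 152 | 1.24 | 1.11 |
| 400 clinical referrals | 400 × 0.25 + 400 × 0.01 = 104 | 1.81 | 1.34 |
| First 105 all cytology, remaining 695 by workload | 336.7 × 0.25 + 463.3 × 0.01 = 88.8 | 2.12 | 1.46 |
| All 800 by workload | 72 | 2.61 | 1.62 |

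**The case against.** The strongest reply is that the sections can be read together: 4.3.1 states an aim and describes who is eligible, while 7.1 sets the numbers. On that reading 533 clinical-indication women would never be recruited. This stands in part. The workload mix is an upper scenario, and the effect shrinks quickly with fewer clinical referrals. But 4.3.1 speaks of all such women, nothing refers the recruiter to a quota, and the figures in section 2 rule out 50 as the natural result.

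Several stronger readings are tempting, and the documents do not support them.

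- **That the intervals differ 2.6-fold.** Only the number of diseased women does. Width goes with the square root, so sensitivity widens about 1.6-fold, and specificity moves slightly the other way.
- **That a promised precision is broken.** Section 7.1 states no width, so 7.8 points cannot be called a failure against a target. The endpoint in 4.2 is not an interval width either.
- **That 4.3.1 alone would fill the study with disease-free women.** At p = 25%, 612 of 800 (76.5%) are disease-free under the 7.1 mix too.
- **That the PPV and NPV would describe the wrong population.** The prevalence adjustment in 7.2 largely answers this. It does not replace diseased women lost to the sensitivity estimate.
- **That the statement about no power calculation is false and should be deleted.** A calculation of interval width is not a power calculation, and the later paragraph appears to have been added after the first year. Both statements may be true; they need to be reconciled.

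**Conclusion.** The conflict between 4.3.1 and 7.1 is real, and the case mix decides how much precision 800 women deliver. In the upper scenario diseased women fall from about 150-226 to 59-85 (up to about 2.6-fold). The sensitivity half-width widens from 4.4-5.4 to 7.1-8.6 points (about 1.6-fold).

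This rests on three assumptions: recruitment in proportion to workload, the HPV-positive disease rate applied to cytology referrals, and the first 105 women following the same mix. If those 105 were all cytology referrals, the case ratio is about 2.1. With 200 or 400 clinical referrals it is about 1.2 or 1.8.

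The contradiction itself needs only the first step of the working, and no prevalence figure. It should be fixed. It does not show that 800 is too few.

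**What to change.** 1. Reconcile 4.3.1 with 7.1. The simplest way is to limit clinical-indication recruitment in 4.3.1 to the roughly 50 that 7.1 states and to track it with a running count. If the sponsor wants more of these women, revise the split in 7.1 instead and restate the precision for it.
2. In 7.1, reconcile the statement that no formal power calculation was made with the later calculation for 800.
3. In 7.1, have the sponsor state its own assumed prevalence, expected number of diseased women and interval width for the chosen mix. The widths shown above rest on assumptions and should not be inserted as the sponsor's justification.

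The cost is protocol wording and a recruitment counter. The downside of the limit is fewer women from a group that section 2 names as likely to benefit. About 50 × 0.01 = 0.5 diseased women would be expected among them, so sensitivity could not be estimated in that group.
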